Secondary (outcome analysis) - The proportion of patients over-triaged by physicians in the game-based training group will be equivalent to the proportion over-triaged by physicians in the usual care group

Secondary (mediation) - Under-triage will mediate the effect of the intervention on patient-centered outcomes.

Exploratory (heterogeneity of treatment effect) -

- [1] The intervention will have the same effect on males as on female trial participants.
- [2] The intervention will have the same effect on White compared as on non-White trial participants.
- [3] The intervention will have a greater effect on trial participants who expressed positive attitudes to game-based learning before enrollment compared to those who do not have positive attitudes.
- [4] Trial participants in the game-based training group who use Night Shift 2024 for greater than 2 hours will under-triage a smaller proportion of severely injured patients than those who use the game for less than 2 hours.
- [5] The proportion of patients under-triaged by trial participants will be lower immediately after exposure to the intervention (i.e., in the first 30 days) compared to late post-exposure period (i.e., 30-89 days).
- [6] Trial participants with greater parameters of compliance on SONAR (the experimental tool to measure determinants of physicians' decision making) will under-triage a smaller proportion of severely injured patients than those with lower parameters of compliance.

**2. \* Describe the relevant prior experience and gaps in current knowledge including preliminary data. Provide for the scientific or scholarly background for, rationale for, and significance of the research based on existing literature and how it will add to existing knowledge:**

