		5.2.1	Secondary outcome measure of functional independence delayed	Cost of data purchase
1.4	9/29/25	7.5	Primary analysis will not include baseline covariates or random effects for the hospital	Parsimony; model stability
		7.7	Add a complier average causal effect analysis (CACE) to per protocol analysis to test the effect of study protocol compliance	Robustness
		7.10	One-sided alpha changed to a two-sided test	Improve rigor of interpretation
DATA LOCK OCCURS – October 1, 2025				
1.5	10/3/25	5.3	Re-defined dose as game usage during each intervention period instead of based on time spent.	Improve understanding of mediation
		7.1	Remove exploratory analysis of fidelity of intervention receipt; remove mediation analysis of clinical outcomes	Inability to acquire correct statistical package on CMS Virtual Desktop; results preclude necessity

SUMMARY

Study Population: The primary study population consists of 800 board-certified emergency physicians employed at non-trauma centers in the continental US. Outcomes are assessed using Medicare claims from patients aged 65 or older treated by trial physicians during the one-year post-enrollment period.

Design: This is a Phase 3, Type 1 hybrid effectiveness-implementation randomized clinical trial in which physicians are randomized 1:1 to play *Night Shift 2024* (game-based training) or to receive usual education (control). The primary outcome is assessed using Medicare claims data collected for 13 months after the close of enrollment.

Sample Size: A total of 800 physicians (400 per arm) provides 80% power to detect a 7.4% to 10% absolute reduction in under-triage at a one-sided significance level of 0.05, assuming an intraclass correlation coefficient of 0.45 and a median of 1-2 eligible patients per physician.

TABLE OF CONTENTS

1. ABBREVIATIONS	7
2. BACKGROUND AND RATIONALE	8
3. ENROLLMENT CRITERIA	8
3.1. Physician Participants	8
3.1.1. Inclusion criteria	9
3.1.2. Exclusion criteria	9
3.2. Patient Participants	9
3.2.1. Inclusion criteria	9
3.2.2. Exclusion criteria (primary analysis)	9
3.3. Hospital Characteristics	9
3.4. Key Decision Makers	10
3.4.1. Inclusion criteria (must meet at least one of the following)	10
3.4.2. Exclusion criteria	10
4. INTERVENTIONS	10
4.1. Intervention Arm (Game-Based Training)	10
4.1.1. Dosing and administration	10
4.1.2. Measurement of fidelity of treatment delivery	11
4.1.3. Measurement of fidelity of treatment receipt	11
4.2. Control Arm (Usual Education)	11

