4.1.1. Dosing and administration

Participants are asked to complete a minimum of 2 hours of gameplay within 2 weeks of receiving their device, followed by three 20-minute booster sessions at approximately 4, 7, and 10 months post-enrollment. Participants receive three email reminders and a phone call during the first two weeks, followed by quarterly reminders thereafter. A conditional honorarium of \$20 per completed booster session is provided. Participants also keep the trial iPad at the end of the year, as part of their honorarium.

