4.1.2. Measurement of fidelity of treatment delivery

We define fidelity of treatment delivery as adherence to the study protocol. The application automatically records time spent, number of visits, and progress through the game. These data are uploaded to a secure University of Pittsburgh server each time the device connects to a wireless network. Participants are additionally asked to self-report game usage and complete the User Engagement Scale Short Form (a validated 12-item instrument) after completing the first 2 hour game-play session.

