7.7.3. Mediation of the game's effect on under-triage

We test 4 mediators of the treatment effect: intervention dose (≥ 2 hours versus < 2 hours), timing of game use–treatment of patient (≤ 30 days versus 39-90 days versus > 90 days versus none), and fidelity of intervention receipt (perceptual sensitivity and decisional threshold). To evaluate exposure–effect relationships, we model the probability of under-triage and included an interaction term between the mediator and patient injury severity. To evaluate fidelity of intervention receipt relationships, we conduct a causal mediation analysis to assess whether the effect of the intervention on under-triage is mediated through perceptual sensitivity (i.e., diagnostic ability – targeted by the game) or by decisional threshold (i.e., willingness to transfer). The total effect of the intervention is decomposed into natural direct and natural indirect effects representing pathways independent of and operating through the mediator.

Protocol Deviation (Version 1.5): We deferred the mediation analysis testing the influence of fidelity of intervention receipt because we could not obtain the correct statistical package to run the analysis on the CMS Virtual Desktop. We also reconceptualized dose as the number of intervention periods during which game play occurred for any amount of time (out of 4 total). Dose therefore represented actual treatment and not assignment.

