10. APPENDIX

10.1. Comparison of analytic elements across study documents.

Domain	DSMB protocol	Manuscript	Status	Rationale
Core Design Elements				
Primary outcome	Under-triage of severely injured patients (i.e., those with an ISS ≥ 16)	Under-triage of severely injured patients (i.e., those with an ISS ≥ 16)	Consistent	No change
Secondary outcomes	Over-triage; Mortality/readmission; Functional dependence*	Over-triage Mortality/readmission	*Deferred	SNF claims not available
Follow up	01/01–12/31/2024 (V1) 365 days (V1.2)	365 days	Consistent	No change
Analysis population	Intention-to-treat	Intention-to-treat	Consistent	No change
Unit of analysis	Patient	Patient	Consistent	No change
Statistical model	Mixed-effects logistic regression	Mixed-effects logistic regression	Consistent	No Change
Clustering	Physician-level and hospital-level random effects (V 1) Physician (V 1.4)	Physician-level	Consistent	No change
Covariate adjustment	Patient, physician, hospital (V1) None (V1.4)	None	Consistent	No change
Repeated measures	Sensitivity analysis	Sensitivity analysis	Consistent	N/A
Power calculation	Detailed	Overview only	Consistent	N/A
Alpha level	0.05	0.025	Deviation	Discussed in the methods
Sidedness of tests	One-sided	Two-sided	Deviation	Discussed in Methods
Multiplicity control	Not done	Not done	Consistent	N/A
Reporting and Secondary Analyses				
Effect modification	Sex, race, attitudes to video games	Sex, race, attitudes to video	Consistent	Simplify manuscript
Mediation analysis	Dose, game use–time to treatment of patients	Dose, game use–time to treatment of patients	Consistent	No change
Mediation analysis	Fidelity of intervention receipt	Not done	Not performed	Statistical package not available
Mediation analysis	Effect of under-triage on clinical outcomes	Not done	Not performed	No difference in clinical outcomes

Domain	DSMB protocol	Manuscript	Status	Rationale
Sensitivity analyses	None (version 1) Multiple (version 1.7)	Multiple	Expanded	Increase rigor

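### Version 1.5, dated after data lock, replaced the 2-hour dose contrast with a count of periods with any play, so Protocol exploratory hypothesis [4] is no longer tested

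*SAP*

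**What the plan says.** The Protocol (Study Aims, exploratory hypothesis [4]) predicts that game-arm physicians "who use Night Shift 2024 for greater than 2 hours will under-triage a smaller proportion of severely injured patients" than those who use it for less. SAP 7.7.3 carries this forward as "intervention dose (≥ 2 hours versus < 2 hours", and SAP 5.3.2 lists the same cut.

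SAP 4.1.1 asks each game-arm physician for "a minimum of 2 hours of gameplay within 2 weeks of receiving their device, followed by three 20-minute booster sessions". SAP 4.1.2 states: "The application automatically records time spent, number of visits, and progress through the game".

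The Revision History Table contains the line "DATA LOCK OCCURS – October 1, 2025". Below it comes Version 1.5 (3 October 2025), whose entry for section 5.3 reads "Re-defined dose as game usage during each intervention period instead of based on time spent". The reason given is a better understanding of mediation. The deviation note in 7.7.3 redefines "dose as the number of intervention periods during which game play occurred for any amount of time", with four periods in total, and adds that dose then reflects actual treatment and not assignment. The note in 5.3.2 says the same.

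Appendix 10.1 lists "Dose, game use–time to treatment of patients" identically for the DSMB protocol and the manuscript, and marks the row as consistent with no change.

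**The concern.** A stated hypothesis has lost its test, and the replacement measures something else. Hypothesis [4] is about time spent playing. The new score discards time: a login of a few seconds counts as much as a completed session, and the first period, where 2 hours are requested, counts the same as a 20-minute booster. The score can therefore rank physicians in the opposite order to their minutes of play, and a flat or inverted dose-response would be hard to interpret.

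Timing adds to this. The change is dated after lock, in a version that also removed an analysis in light of results. A reader who relies on the Appendix row would not learn that the definition had changed.

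**Working it through.** **Inputs.** Requested play: 120 minutes plus three boosters of 20 minutes (SAP 4.1.1). Pre-specified rule: total play of at least 120 minutes versus less (SAP 7.7.3). New rule: number of periods with any play (SAP 7.7.3, Version 1.5).

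**Reproducing the plan's figure.** 1 initial period + 3 booster periods = 4, which matches the stated total of four. Requested minutes: 120 + 3 × 20 = 180.

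**Scoring usage patterns under both rules.**

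| Pattern | Minutes | Share of 180 | 2-hour rule | Period count |
|---|---|---|---|---|
| 1 minute in each of four periods | 4 | 2.2% | under 2 h | 4 |
| Four 1-minute logins, all in one period | 4 | 2.2% | under 2 h | 1 |
| Three boosters, no initial session | 60 | 33.3% | under 2 h | 3 |
| Initial session only | 120 | 66.7% | 2 h or more | 1 |
| Initial session + 1 booster | 140 | 77.8% | 2 h or more | 2 |
| Initial session + 2 boosters | 160 | 88.9% | 2 h or more | 3 |
| Full schedule | 180 | 100% | 2 h or more | 4 |

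Four minutes spread over four periods scores the same as the full schedule and above 160 minutes. Against the single complete session it has 4/120 = 3.3% of the play time but a score of 4 rather than 1. The initial session is 120/180 = 66.7% of requested minutes and 1/4 = 25% of the maximum score. The reversal requires the brief logins to fall in different periods; four in one period score 1.

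**Does another analysis test hypothesis [4]?**
- The per-protocol analysis (SAP 7.3.2, 7.7.1) keeps the 2-hour threshold but compares players of at least 2 hours with usual education.
- The CACE analysis (SAP 7.7.1) classes game-arm physicians as non-compliers only if they never opened the game.
- Neither compares longer with shorter play within the game arm.

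**What was known when Version 1.5 was written?** Lock was on 1 October 2025 and Version 1.5 is dated 3 October, two days later. In the same version, SAP 7.7.4 drops the mediation analysis of clinical outcomes because the game was found not to affect them. Some outcome results were therefore known. No passage says that the relation between dose and under-triage had been examined.

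**How does the Appendix treat other amended elements?** Follow-up, clustering and covariate adjustment also changed and are also marked consistent with no change, but their rows show each definition with its version number. The dose row shows none.

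**The case against.** The case for the period count has substance. The intervention was designed as repeated exposure, with levels released through the year and three boosters, and a count of periods captures spacing that a 2-hour cut misses: under that cut 120 and 180 minutes are the same. Both measures are coarse, and both compare self-selected groups. This supports keeping the count as an additional analysis. It does not support dropping the pre-specified contrast, since time is logged automatically and no defect in those data is cited. Logged hours also describe actual treatment rather than assignment, so the reason in 7.7.3 does not separate the two measures.

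The four one-minute logins are a constructed extreme. That stands: the documents report no usage data, and SAP 7.7.3 does not say whether the count enters as a linear or a categorical term.

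Two stronger readings are tempting. A reader might infer that the new dose definition was chosen after the dose results had been seen. The documents show only that clinical-outcome results were known. SAP 6.2 keeps analysts masked throughout the analysis, and SAP 7.10 refers to an interval between lock and unmasking. A reader might also infer that the Appendix conceals the change. The table compares the DSMB protocol with the manuscript, other amended rows carry the same status wording, and the dose change is disclosed in the Revision History Table, 5.3.2 and 7.7.3. The defect is the missing version history in that row.

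Finally, the dose analysis is exploratory and hypothesis-generating (SAP 7.7). That is correct and limits the weight of the point.

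**Conclusion.** The point holds as a matter of analysis choice and reporting. The pre-specified dose contrast was replaced after data lock by a score with no duration floor, and hypothesis [4] is left without a test. On the requested schedule the new score can place 4 minutes of play above 160; how often this occurs is unknown. Blindness of the redefinition to results cannot be assumed, but the text goes no further than that.

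The conclusion rests on two assumptions: that any logged play, however short, counts toward a period, as the wording says, and that the app's time records are usable, which SAP 4.1.2 implies and nothing contradicts. The primary, secondary and safety analyses are unaffected.

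**What to change.** 1. Report the 2-hour contrast among game-arm physicians, using app-logged time, as the dose analysis for hypothesis [4]. State which boundary is used: the Protocol says more than 2 hours, the SAP at least 2 hours.
2. Keep the period count as a supplementary analysis labelled *defined after data lock (Version 1.5)*.
3. In the Appendix 10.1 dose row, show the 2-hour cut in Version 1 and the period count in Version 1.5, after lock, in place of the unqualified status.
4. An analysis of cumulative minutes is optional. It appears in neither document, so it too must be labelled post hoc.

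The SAP is a reconstruction that says it introduces no new analyses. The 2-hour contrast is not new, and its result can go in the report or a dated addendum, leaving the record of deviations intact. The cost is some wording, one run of an exploratory model on data the app is stated to record, and one more exploratory result to report.

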7.7.4. Mediation of the game's effect on clinical outcomes

We test whether the game exerts its effect on clinical outcomes through the pathway of under-triage, using a causal mediation analysis as above. Again, we decompose the effect of the game on clinical outcomes into direct and indirect effects representing pathways independent of and operating through the mediator.

Protocol Deviation (Version 1.5): We eliminated this mediation analysis testing once we recognized that the game did not influence clinical outcomes.

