2. BACKGROUND AND RATIONALE

Trauma disproportionately affects older adults, who account for nearly half of all injury-related hospital admissions and two-thirds of in-hospital injury-related deaths in the United States. The cornerstone of trauma care is timely transfer of severely injured patients to trauma centers, where mortality is reduced by 10-25% and rates of return to independent living are substantially improved. Guidelines from the American College of Surgeons specify the injury patterns that warrant transfer. Despite four decades of quality improvement efforts, under-triage (the failure to transfer severely injured patients) remains common, affecting approximately 50% of patients at non-trauma centers overall and more than 80% of patients over the age of 65.

Physicians represent the largest identifiable source of variation in triage practices, accounting for up to 40% of the variance in transfer decisions. A critical but underappreciated driver of this variation is diagnostic error rooted in poorly calibrated clinical heuristics. Older trauma patients frequently lack the classic physiologic markers of severe injury (hypotension, tachycardia, penetrating wounds) that trigger pattern recognition in physicians trained on younger populations. Compounding this, ED physicians at non-trauma centers rarely encounter severely injured patients (approximately 1 in every 1,000 presentations), receive delayed or no feedback on their triage decisions, and are therefore unable to accumulate the experience needed to recalibrate their intuitive judgments. Existing educational interventions, including Advanced Trauma Life Support (ATLS), are designed around a rational actor model of decision making and have had limited impact on real-world triage behavior.

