6.2. Blinding

Full blinding is not possible in this trial given the nature of the intervention. Participants are aware of their assigned arm following allocation. However, data analysts are kept masked to treatment assignment throughout the analysis period to minimize the risk of bias in outcome assessment.

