7. STATISTICAL ANALYSIS PLAN

7.1. Statistical Objectives

The primary statistical objective is to determine whether physicians randomized to *Night Shift 2024* under-triage a smaller proportion of severely injured older patients compared to those receiving usual education, as assessed using Medicare claims data over the one-year post-

enrollment period. Secondary objectives are to evaluate the effect of the intervention on patient outcomes (30-day mortality and readmissions, functional dependence) and to assess safety (over-triage).

Exploratory objectives include evaluating: 1) the heterogeneity of treatment effect across pre-specified physician-level subgroups; 2) the mediation of the intervention's effect by dose, time between game usage and treatment of patient, and fidelity of intervention receipt; 3) the mediation of clinical outcomes by the intervention

Protocol Deviation (Version 1.3 and 1.5): We did not assess the effect of the game on functional dependence, mediation by fidelity of intervention receipt, or mediation by the game.

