7.7. Exploratory Analyses

These analyses are hypothesis-generating and are not adjusted for multiple comparisons. Full results of these analyses, including interaction term estimates, standard errors, and 95% confidence intervals will be reported.

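### The protocol's secondary hypothesis that under-triage mediates patient outcomes was dropped after data lock because the clinical result was null, which is not a valid reason

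*SAP*

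**What the plan says.** The protocol, under Study Aims, states: "Secondary (mediation) - Under-triage will mediate the effect of the intervention on patient-centered outcomes". It sits there with the other secondary hypotheses, separate from the exploratory ones.

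The SAP places the same analysis lower. Section 7.1 lists it third among the exploratory objectives, loosely worded as "the mediation of clinical outcomes by the intervention". Section 7.7, which contains it, opens with "These analyses are hypothesis-generating and are not adjusted for multiple comparisons". Section 7.7.4 gives the substance: a causal mediation analysis, by the method of Section 7.7.3, splitting the game's effect on clinical outcomes into a part that runs through under-triage and a part that does not. No row of the SAP's revision history explains why a secondary hypothesis in one document is exploratory in the other.

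The revision history puts data lock at 1 October 2025 and version 1.5 at 3 October 2025. Section 7.7.4 gives the reason for the removal made in that version: "We eliminated this mediation analysis testing once we recognized that the game did not influence clinical outcomes". The revision row covers two removed mediation analyses and gives two reasons, an unavailable statistical package and "results preclude necessity". The Appendix separates them: the package is the reason for the fidelity-of-receipt mediation, and the absence of a clinical difference is the reason for this one. The SAP shows no estimate, interval or p-value for the clinical outcome, and no result for under-triage.

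**The concern.** By the SAP's own account, a hypothesis stated in advance was dropped because of a result already seen. Reports of hypotheses are only interpretable as a set if the decision to analyse does not depend on the data.

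The reason given is also unsound. The total effect combines a direct and an indirect effect. A total near zero can arise because both are zero, because they oppose each other, or because the estimate is too imprecise to show a real but small effect. Only the first leaves nothing to decompose, and a null comparison cannot tell the three apart.

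Two things are at stake. The specific link from better triage to better outcomes, which the protocol set out to examine, goes unreported. And a comparison with very little information on that link is turned into a statement that the game had no influence.

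**Working it through.** **The plan's only power figure.** SAP Section 7.2 states a detectable difference in under-triage of 7.4-10 points (80% power, one-sided 0.05). Effective patients per arm are n_eff = physicians x m / (1 + (m - 1) x ICC), with ICC 0.45.

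- 300 physicians (75% of 400), m = 1: n_eff = 300.
- 300 physicians, m = 2: n_eff = 600 / 1.45 = 414.
- 400 physicians, m = 2: n_eff = 800 / 1.45 = 552.

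The baseline rate is not stated as an input, so exact reproduction is not possible. A two-proportion calculation is consistent with the range: at a baseline near 62%, n_eff 300 gives 10 points and n_eff 552 gives 7.4; at a baseline of 80%, n_eff 414 gives 7.3. No power is stated for the clinical composite.

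**Expected total effect on the composite if the hypothesised pathway is real.**

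- Fall in under-triage: 7.4-10 points (SAP 7.2).
- Relative benefit of trauma-center care: 10-25%. SAP Section 2 gives this for mortality; carrying it over to death or readmission is an assumption.
- Composite risk: 20-40%. This is an assumption; the documents give none.

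Total effect = fall in under-triage x risk x relative benefit.

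- Smallest: 0.074 x 0.20 x 0.10 = 0.0015, or 0.15 points.
- Largest: 0.10 x 0.40 x 0.25 = 0.010, or 1.0 point.

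**Precision.** SE = sqrt(2 x risk x (1 - risk) / n_eff), using the under-triage ICC for the composite as well.

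| n_eff per arm | risk 20% | risk 40% |
|---|---|---|
| 300 | sqrt(0.32/300) = 3.3 points | sqrt(0.48/300) = 4.0 points |
| 414 | sqrt(0.32/414) = 2.8 points | sqrt(0.48/414) = 3.4 points |

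**Power, two-sided 0.05.** Most favorable corner: 1.0 / 3.4 = 0.29 standard errors, power 6.0%. Least favorable: 0.15 / 3.3 = 0.05 standard errors, power 5.0%. The 95% interval would have a half-width of 1.96 x 2.8 = 5.5 to 1.96 x 4.0 = 7.8 points. For 80% power the comparison would need about 37,500 to 1.14 million effective patients per arm.

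The ICC choice hardly matters. With no clustering at all (n_eff 600), the best corner is 1.0 / sqrt(0.48/600) = 1.0 / 2.8 = 0.35 standard errors, and power is still about 6%.

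**Does a null total effect imply a null indirect effect?** A simulation routed the whole effect through under-triage: 2,000 trials per setting, independent patients at the effective sample size, and an assumed 25% event risk if transferred. It compared the total-effect test with a joint-significance test of the indirect effect, both at two-sided 0.05. Selected settings:

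| n_eff | baseline under-triage | fall in under-triage | assumed transfer benefit | total-effect test rejects | indirect-effect test rejects |
|---|---|---|---|---|---|
| 300 | 50% | 7.4 points | 2.5 points | 5% | 4% |
| 300 | 80% | 7.4 points | 5 points | 5% | 13% |
| 414 | 50% | 7.4 points | 10 points | 6% | 49% |
| 414 | 50% | 10 points | 10 points | 6% | 73% |

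Over all settings run, the total-effect test rejected in 4-6% of trials and the indirect-effect test in 4-73%. The simulation is illustrative: it does not fit the planned mixed model and has no mediator-outcome confounding.

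**The case against.** The strongest reply is that the sponsor hid nothing. The revision history, Sections 7.1 and 7.7.4 and the Appendix all report the removal, and the reason makes plain that clinical results were known. That stands, and no further record of the deletion is needed. Disclosure does not make the reason valid.

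Second, both documents speak of mediating or decomposing an effect of the game, so skipping the step when no effect is seen is an understandable habit. The habit requires the total effect to be informative, and here it was not. A null effect on under-triage itself would have been a much better reason, but the SAP does not give it.

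Third, the remedy has limits. Transfer was not randomised. The transfer-outcome association in claims is open to confounding by severity and prognosis, and the indirect effect would often be imprecise: at n_eff 414 with a 7.4-point fall, the simulated test rejected in only 7-55% of trials. Section 7.7.4 names no confounders, so some choices would now be made with results known. All of this stands. It limits what the analysis can show, and does not justify leaving it out.

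Fourth, Section 7.7.4 relies on the method that Section 7.7.3 says could not be run for want of a package. The same obstacle may well have applied here, but Section 7.7.4 and the Appendix cite only the result.

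A reader might also infer that the masking in Section 6.2 was broken, since "data analysts are kept masked to treatment assignment throughout the analysis period". The documents do not show this: a lack of difference can be seen with coded arms.

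**Conclusion.** The point holds. A protocol secondary hypothesis was removed after data lock because of the observed clinical result, and that result is not a valid ground for removal. Under the stated assumptions the clinical comparison had about 5-6% two-sided power for the effect the pathway could produce, so a null was the expected finding whether or not the pathway works. The size rests on the assumed 20-40% composite risk and on carrying the mortality benefit over to the composite. The logical point rests on neither.

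Three stronger readings are not supported. A reader might infer that the link from the game to patient outcomes went untested, but the randomised comparison on 30-day death or readmission is retained (SAP 7.6.1 and Appendix). What is missing is the split through under-triage. A reader might infer that the hypothesis was demoted once results were in. The documents show only that the labels differ and that no revision row explains it; the SAP was reconstructed from the DSMB protocol, which may have carried the exploratory label from the start. And although a non-significant test is the natural reading of the clinical result, the SAP gives no p-value.

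The primary analysis is unaffected. This is a correction that should be made, not a threat to the main conclusion.

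**What to change.** 1. Run the Section 7.7.4 decomposition for the 30-day composite and report direct and indirect effects with 95% intervals that account for clustering by physician, whatever they show. Functional dependence was not measured, so it cannot be included.
2. Label any confounder set or estimation method not written in Section 7.7.4 as chosen after results were known. Adjustment for ISS, age and comorbidity, with logistic models and standardisation, would be such a choice.
3. State that the transfer-outcome link is not randomised, that the decomposition assumes no unmeasured mediator-outcome confounding, and that the indirect effect may be imprecise.
4. Replace the statement of no influence on clinical outcomes with the risk difference and its 95% interval.
5. Reconcile the secondary label in the protocol with the exploratory label in the SAP, and say which governs.
6. If the analysis is still omitted, give a reason that does not depend on the clinical result. If the missing package was the real obstacle, say so.

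The cost is modest analyst time inside the CMS environment, provided access continues, which the documents do not state. The price in interpretation is wide intervals and an untestable confounding assumption.
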